8.4.4 Exploratory Analysis

In addition to the primary ITT analyses described above, we will conduct an "as treated" analysis in order to evaluate those who completed the study and received at least 80% of treatments. We will evaluate the effects of indirect costs (i.e., co-pays), treatment center, season, geography, and psoriasis characteristics (such as plaque thickness) on response rate. Additional exploratory analysis will be conducted by request of our stakeholder committees upon review of the data (these will be designated post hoc). Exploratory and post hoc analyses will be interpreted with caution and taking into consideration the total number of post hoc comparisons that have been conducted.

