Phototherapy is a preferred first line treatment because oral medications can result in serious organ damage and/or significant gastrointestinal intolerance and biologics suppress the immune system and have warnings for infections and malignancy²¹²². Phototherapy was first used to treat psoriasis in the 1920s and is a widely accepted standard of care²³. In the 1980's split body studies demonstrated that NB-UVB (311 nm) was more efficacious than traditional broadband (290-320 nm) ultraviolet B (UVB) phototherapy²³. It is important to distinguish narrowband phototherapy, which can be delivered via medical devices in the home or office, from commercial tanning beds which deliver predominantly ultraviolet A radiation and are ineffective for psoriasis. Guidelines of care issued by the American Academy of Dermatology highlight that NB-UVB phototherapy is a widely accepted, first line, standard of care treatment and also indicate that patients with psoriasis who are compliant, motivated, and adherent with instructions and follow-up examinations could, under dermatologist supervision, be considered appropriate candidates for home NB-UVB therapy²³. Phototherapy remains a critical therapeutic modality that is much more widely prescribed by dermatologists than systemic treatments such as biologics (which are prescribed only by an estimated 20% of dermatologists)²⁴. Although phototherapy does not treat psoriatic arthritis (PsA), it is often used to augment response to systemic agents and the majority of patients do not have PsA^{23, 25}. Despite home phototherapy being highly preferred by patients, as summarized by a recent review of psoriasis treatment for UptoDate, "uncertainty regarding the safety of home units has led to a reluctance to prescribe them."²⁶ NB-UVB requires treatments three times per week for 12 weeks in order to achieve optimal skin clearance. Treatment may then continue on a maintenance basis (1-2 times per week) or be stopped and then restarted when psoriasis recurs and is symptomatic enough that the patient desires another course of phototherapy²⁷. As a result, office based phototherapy is highly burdensome for patients who need to take time off from work and family to receive treatment. Moreover, only about 10% of counties in the US offer office based phototherapy²⁸.

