5.7 Subject Compliance Monitoring

Compliance will be measured by evaluating the number of study treatments received. Patients receiving home phototherapy will have this recorded by the home phototherapy device. Home phototherapy treatments will be verified via software obtained from the device upon their return to Daavlin. The data obtained from the devices will be considered the primary data for analysis. Patients randomized to office based phototherapy will have their treatments entered by the site staff. It is expected that patients will receive up to 36 treatments. Patients who receive at least 29 treatments will be viewed as compliant for the purposes of sensitivity analyses.

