8.2 Secondary Endpoints

In addition to pooled analyses described above, separate analyses will be conducted for each skin type using a non-inferiority margin of 15%. The estimated risk difference in dichotomized DLQI at week 12 and PGA at or before week 12 will be estimated empirically based on the proportion of patients achieving the endpoint in each skin type sub-group and study arm. We will also assess heterogeneity of treatment effect (HTE) across the three skin types using logistic regression. In this analysis, we will fit models for each of the two primary outcomes with skin type, treatment arm, and their interaction as predictors. HTE will be assessed using an omnibus Wald test of all interaction regression parameters for each outcome of interest in order to minimize multiple testing and consequent alpha inflation.

In secondary analyses, we will investigate additional outcomes:

- Total number of phototherapy treatments received
- Cumulative dose of phototherapy
- Frequency of topical concomitant psoriasis treatment
- Changes in initiation, dosing, or discontinuation of oral or biologic psoriasis treatments
- Patient-reported amount of time spent on phototherapy
- Patient reported travel (cost and time)
- DLQI score of ≤1at week 12

- MCID on DLQI at week 1245
- Physician reported change in the product of body surface area (BSA) times PGA (both as a continuous measure and as a dichotomous measure evaluating a 75% and 90% reduction in the BSAxPGA).
- Duration of treatment response
- Percentage of patients receiving ≥ 80% of assigned treatments

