Duration of response will be measured in patients who achieved a DLQI score of 5 or less at week 12, are no longer receiving phototherapy, and who have not initiated a new systemic treatment or had dose escalation of an existing psoriasis systemic treatment at any point during the study. Duration of response will be defined as the length of time from week 12 to the earliest of DLQI > 5 or time of initiation of a new systemic treatment or dose escalation of an existing systemic treatment, with patients who maintain DLQI \leq 5 throughout the 12 week observation period with no new systemic treatments or dose escalation censored at week 24. In order to obtain results that are generalizable to the full ITT study population, we will use inverse probability weighting to account for possible selection bias due to differences between characteristics of participants included in this analysis and the full study population. Duration of response will be analyzed using a Cox proportional hazards regression model adjusted for treatment arm, skin type, and their interaction. Based on results for the interaction term between study arm and skin type, we will report differences in duration of treatment response between study arms by skin type.

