8.5 Subject Population(s) for Analysis

The primary analysis will be based on all subjects randomized into the study, regardless of whether they received the assigned treatment. We will also conduct an "as treated" analysis in order to evaluate those who completed the study and received at least 80% of treatments

9 Safety and Adverse Events

Designated site personnel at each site have the front-line responsibility of reviewing patient-reported response to phototherapy, identifying and documenting treatment emergent adverse events, and adjusting phototherapy dosing accordingly. The Sponsor/Study Principal Investigator is responsible for tracking these reports and relaying them, if required, to the IRBs and other investigators. For this pragmatic study, where intervention is standard of care and performed by the patient's clinician or the patient themselves (in the case of home treatment), AE's not related to phototherapy are not required to be recorded or followed by patient's clinician and will not be recorded for study purposes.

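### The only adherence-based analysis of the primary outcomes is restricted to a post-randomization subset, and no handling of selection into that subset is specified.

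*Combined protocol and SAP*

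**What the plan says.** Section 8.4.4 adds to the primary ITT analysis an *as treated* "analysis in order to evaluate those who completed the study and received at least 80% of treatments", and 8.5 repeats the same set. Section 5.7 uses the same cut-off: "It is expected that patients will receive up to 36 treatments" and "Patients who receive at least 29 treatments will be viewed as compliant for the purposes of sensitivity analyses". None of the three sections names a model, covariates, weights or an estimand for this comparison.

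Two parts of 8.2 bear on it. The list of secondary outcomes includes "Percentage of patients receiving ≥ 80% of assigned treatments", so adherence is itself to be compared between arms. For duration of response, which is also analysed in a subset formed after randomization, the plan says "we will use inverse probability weighting to account for possible selection bias".

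On burden, 1.1 states that "office based phototherapy is highly burdensome for patients who need to take time off from work and family to receive treatment". Section 13.3 says that travel and co-pays are not reimbursed, while 12.2 and 12.3 say that the home machine is free to the patient.

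**The concern.** Randomization balances the arms as randomized. It does not balance those who go on to complete the study with 80% of treatments. If the share or the kind of patient reaching 80% differs by arm, and adherence is related to response, the home and office adherers differ for reasons other than the treatment setting. A difference among adherers can then appear where none exists, or a real one can be hidden.

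Readers of a non-inferiority trial commonly look at an adherent-set result to see whether poor adherence made the arms look alike under ITT. A comparison distorted by selection could seem to contradict the primary result, or give it support it has not earned. The plan recognizes this kind of problem for duration of response and prespecifies a tool for it, but does not extend that tool to the adherent set.

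**Working it through.** **1. Is this the only adherence-based check?** The threshold in 5.7 is 29/36 = 80.6%, and 0.80 × 36 = 28.8, which rounds up to 29. So 5.7, 8.4.4 and 8.5 describe one rule. The tipping-point analysis in 8.4.5 varies missing values, not adherence. The answer is yes.

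**2. The plan's own sample size (8.3).** With 50% response in both arms, a 15-point margin, one-sided 2.5% and 80% power:

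n per arm = (1.960 + 0.842)² × (0.25 + 0.25) / 0.15² = 174.4, rounded up to 175.

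This reproduces the stated figure. It applies to ITT and does not bear on the adherent set.

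**3. Illustrative size of the selection error.** All inputs are assumptions, since the documents give no adherence by arm. Let X be one standard normal baseline factor, and let the arms have identical effects.

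- logit P(adhere | X) = a + βX, with a set separately in each arm to give the assumed share reaching 80%.
- logit P(respond | X) = c ± βX, with c set so that overall response is 55% in both arms.
- β = ln(OR), with OR 1.5, 2.0 or 2.5 per SD.
- Response among adherers = E[P(adhere | X) × P(respond | X)] / E[P(adhere | X)].

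Example with 60% v 35% and OR 2.0: home adherers respond at 58.9% and office adherers at 61.3%, a difference of −2.4 points when the truth is 0.

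| Share reaching 80%, home v office | X raises both (OR 1.5 / 2.0 / 2.5) | X raises adherence, lowers response |
|---|---|---|
| 60% v 25% | −1.3 / −3.4 / −5.3 | +1.4 / +3.6 / +5.7 |
| 60% v 35% | −0.9 / −2.4 / −3.7 | +1.0 / +2.5 / +3.9 |
| 60% v 50% | −0.4 / −1.0 / −1.5 | +0.4 / +1.0 / +1.5 |
| 55% v 50% | −0.2 / −0.5 / −0.7 | +0.2 / +0.5 / +0.8 |

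Entries are home minus office in percentage points. Gaps of 70% v 60% and 80% v 70% give the same 0.4 to 1.5 points as 60% v 50%.

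**4. A second model.** Here adherence and response are correlated normal variables with correlation ρ from any source, measured or not, and true response is 50% in both arms. At 80% v 70% the error is −1.2 points (ρ = 0.2) to −3.2 (ρ = 0.5). At 80% v 50% it is −3.6 to −9.6, and +5.5 at ρ = −0.3. It is zero when adherence is equal or when ρ = 0. The two models agree on the pattern; the size depends on the adherence gap and on how strongly adherence is tied to response.

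**5. What it could do to the adherent-set result.** Take 525 per arm (1050/2), response about 50%, and 60% v 35% adherent, giving 315 and about 184 patients.

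- SE = √(0.25/315 + 0.25/184) = 0.0464.
- Chance of meeting the margin with no bias: Φ(0.15/0.0464 − 1.96) = 90%.
- With a bias of −2.4 points: Φ(0.126/0.0464 − 1.96) = 78%.

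At 60% v 25% with a bias of −3.4 points, the fall is from 82% to 61%.

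**The case against.** The case on the other side is substantial.

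- **Reaching 80% is far harder in the office.** A reader might infer this from 1.1 and 13.3, but the documents support a direction at most. Section 4.1 requires every patient to be able to travel to the office about three times a week. Section 4.2 excludes those who cannot or will not comply for time, work, school or financial reasons. Section 3.1.1 has patients confirm that they accept office randomization once co-pays are known. No adherence figure by arm is given.
- **The plan commits to an unadjusted comparison.** It does not say so; it is silent. The skin-type-adjusted logistic model of 8.1 may be meant to carry over. What is missing is any stated handling of selection into the set.
- **The non-inferiority conclusion is at risk.** It is not. The conclusion rests on ITT (8.1). The 80% analysis is exploratory, to be read cautiously, and no section gives it a confirmatory role. In a pragmatic trial, differing attendance is part of the effect being compared.
- **The duration-of-response weighting is an imperfect precedent.** Its purpose is to generalize an analysis of selected responders to the full ITT population. It still shows that the investigators accept weighting for a subset formed after randomization.
- **Part of the remedy exists.** The share of each arm receiving at least 80% is already a secondary outcome with a confidence interval.

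These objections limit the size and importance of the point. They do not fill the gap: the set is formed after randomization, the plan treats membership as something that may differ by arm, and it specifies nothing to deal with that.

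**Conclusion.** The gap is real but minor. The only adherence-based analysis of the primary outcomes conditions on a post-randomization event without specifying how selection is handled. Under assumed adherence of 60% v 25% to 35%, and one baseline factor with odds ratio 1.5 to 2.5 per SD, the comparison could be wrong by about 1 to 6 points in either direction. With a 10-point gap the error is about 0.4 to 1.5 points. Stronger links between adherence and response, as in the second model, give more; equal adherence, or adherence unrelated to response, gives none.

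A reader might also infer that the bias necessarily runs against home. The documents do not fix its sign. PGA is read at discontinuation if that comes before week 12 (3.2.1), so a patient who clears early and stops before 29 treatments is an ITT responder left out of the adherent set. That kind of selection can reverse the direction.

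**What to change.** In 8.4.4 and 8.5, keep the unweighted comparison and report beside it a weighted risk difference for each primary outcome:

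- Within each arm, model the probability of being in the adherent set from a short prespecified list of baseline variables, for example travel time and cost, co-pay, PGA, BSA, DLQI and skin type. These are already recorded (6.1, 7.1).
- Weight each adherer by the stabilized inverse of that probability, with a prespecified truncation rule, and give a robust 95% CI against the 15-point margin.
- Do not enter clinic as separate fixed terms. With 20 to 40 sites, about 390 patients per arm ((350 + 350 + 80)/2, from 3.1) and 25% to 35% office adherence, there would be only about 98 to 137 office adherers, and the weights would be unstable.
- Show the share of each arm in the set next to the result.
- State that these weights do not correct for unmeasured motivation, or for early clearers who stop before 29 treatments.

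The cost is a little more analysis with a method already in the plan, and no new data. The downside is a wider interval and only partial removal of the bias, so the weighted result should be presented as a partial correction.

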8.4.5 Missing Data Strategy

Our analysis strategy for the primary outcome of clear/almost clear skin and the patient reported DLQI (no impact on quality of life) uses an ITT strategy by treating all patients who discontinue treatment prior to achieving clear/almost clear skin as treatment failures. Thus, for these outcomes there will be no missing data. For secondary and exploratory analyses of longitudinal outcome measures that require data from follow-up assessments, such as dosing of phototherapy, frequency of concomitant psoriasis treatment, and amount of time spent on treatment, our analysis strategy incorporates all available baseline and longitudinal information. The GEE estimator is only unbiased if data are missing completely at random (MCAR). If the total proportion of observations with missing data in a given analysis exceeds 10%, we will address loss of efficiency due to missing data and possible bias arising from violation of the assumption of MCAR missingness by undertaking multiple imputation (MI) implemented using multiple imputation via chained equations (MICE). Using MICE, we will create 10 imputed versions of the complete data set with all missing outcomes and patient characteristics imputed simultaneously. For each analysis that makes use of data elements with missingness, we will then conduct the analysis in each imputed data set and combine the results using standard rules.

We will conduct additional sensitivity analyses to explore the sensitivity of our results to possible missing not at random missingness. We will use the "tipping-point" approach to identify combinations of values for missing measures that would change the conclusion of our study and will summarize the results using graphical displays.

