3.1 General Design

The design is a large pragmatic randomized active comparator study of home vs. office based NB-UVB phototherapy for the treatment of psoriasis. Both comparator treatments are considered standard of care and thus this would be classified as a Phase IV study. Dosing of phototherapy will be based on a standardized protocol (see APPENDIX A) or a standard protocol that is routinely used by the local investigators in order to reflect routine clinical practice. The study will include up to 1050 patients stratified by Fitzpatrick skin type (350 skin type I/II, 350 skin type III/IV, we anticipate that approximately 80 participants will be enrolled in Skin type V/VI). We hypothesize that home phototherapy will be noninferior to office based phototherapy. There will be a recommended screening period of up to 28 days, to allow for obtaining informed consent and administrative procedures necessary for office based or home phototherapy, as well as randomization. Patients will be randomized (1:1) to home vs. office-based phototherapy within 28 days of the baseline visit or per standard of care of individual practices. If the patient is randomized to home phototherapy a machine will be delivered to their home and phototherapy treatment initiated within 14 days of randomization. If the patient is randomized to office phototherapy, the first treatment should occur within 14 days of randomization. The patient will be assessed by the dermatologist (or PA or NP or other gualified clinician as appropriate to the clinical practice) at baseline and at 12 (plus or minus 2) weeks after start of phototherapy, or at the time of discontinuation of phototherapy, whichever comes first. Patients will receive phototherapy treatments about 3 times per week for 12 weeks. They will then be observed for an additional 12 weeks. With each phototherapy treatment, patient response to prior phototherapy treatment will be collected by clinic staff or recorded on the phototherapy machine via patient assessment. Patients will complete a survey every 4 weeks for the duration of the study that captures patient reported outcomes.

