Because we have no a priori hypothesis of equivalence between treatment arms on these outcomes, these analyses will be conducted using standard hypothesis testing principles. We will report the mean (for continuous measures) or frequency (for binary measures) and 95% CIs for each measure within treatment arms as well as the difference in means or frequencies between treatment arms and the 95% CI of the difference. Secondary outcomes will be measured with a frequency as described in Appendix D, Schedule of Study Procedures. We will analyze these measures using linear or logistic regression models with robust variance estimators via Generalized Estimating Equations (GEE) to account for within-patient correlation that occurs with repeated measures. Regression models will include terms for treatment arm, time since randomization (categorical), skin type, and the treatment arm/time interaction. Inclusion of the interaction term will allow us to assess possible variation in effectiveness of home phototherapy relative to office-based phototherapy over time. Physician reported outcomes (PGA times BSA) will be measured at baseline and at the earlier of week 12 or upon discontinuation of phototherapy, whichever comes first. We will compare this outcome between home and office-based phototherapy arms using linear regression adjusted for skin-type. All secondary analyses will be repeated within each skin type stratum.

During the follow-up observation period, weeks 13-24 after start of therapy, we will compare dichotomized DLQI, and receipt of concomitant topical psoriasis treatment between study arms. These measures will be assessed every four weeks during the observation period and analyses will use the same approach as described above for other secondary outcomes. We will also assess change in oral or biologic psoriasis treatment during the observation period at week 24.

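### Multiple imputation is gated on more than 10% total missingness, which does not show whether the MCAR condition the plan sets for its GEE analyses holds, so outcome-related dropout below the gate can go uncorrected

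*Combined protocol and SAP*

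**What the plan says.** Section 8.2 assigns the repeated secondary measures to GEE: "We will analyze these measures using linear or logistic regression models with robust variance estimators via Generalized Estimating Equations (GEE". It then lists the model terms: "Regression models will include terms for treatment arm, time since randomization (categorical), skin type, and the treatment arm/time interaction". The same approach is carried into the observation period for dichotomized DLQI and topical treatment.

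Section 8.4.5 states the condition for this estimator: "The GEE estimator is only unbiased if data are missing completely at random (MCAR". It gives imputation two purposes, recovering efficiency and dealing with "possible bias arising from violation of the assumption of MCAR missingness by undertaking multiple imputation (MI". Imputation (10 data sets, chained equations) is conditional: "If the total proportion of observations with missing data in a given analysis exceeds 10" percent. No threshold is set by arm, visit or skin type, and no check of MCAR is planned below the threshold.

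Two other statements in Section 8.4.5 limit the reach of the point. For the co-primary outcomes, where non-completers count as failures, it says: "Thus, for these outcomes there will be no missing data". It also adds, with no 10% condition: "We will conduct additional sensitivity analyses to explore the sensitivity of our results to possible missing not at random missingness", using a tipping-point method.

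**The concern.** Whether data are MCAR depends on who is missing and why. The fraction missing does not settle it. A small fraction limits how large the bias can be, but the plan's measure of smallness averages over arms and visits, while the model estimates arm differences visit by visit. Heavy loss in one arm at the last visits can therefore sit inside a total below 10%. In that case the plan reports an estimator that it has itself described as biased and leaves the remedy unused.

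The secondary outcomes are tested for a difference by ordinary hypothesis tests (Section 8.2). A biased contrast would therefore show up as a false finding for home or for office treatment.

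**Working it through.** The 10% threshold is a rule with no calculation behind it, so the plan has no figure here to reproduce. The check asks what the rule lets through.

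**Inputs from the documents.** Allocation: "Patients will be randomized (1:1) to home vs. office-based phototherapy" (Section 3.1). Size: 1050 randomized (Section 4.5), or 525 per arm. If skin type V/VI reaches only about 80, as Section 3.1 anticipates, the total is 350 + 350 + 80 = 780, or 390 per arm. Response rate: 50% in both arms, borrowed from Section 8.3.

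**Assumption not in the documents.** In both arms, missing patients respond g points less often than observed patients. I show g = 0, 10 and 25.

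**What the gate allows.** With equal arms, total missing = (m1 + m2)/2. Both 20% v 0% and 14% v 6% give exactly 10%, which does not exceed the gate.

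**Bias and error rate with no true difference.**
- Bias = (m1 − m2) × g.
- SE = √[0.25/(n(1 − m1)) + 0.25/(n(1 − m2))].
- Two-sided error = P(|Z + bias/SE| > 1.96).

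For 20% v 0% and g = 25, bias = 0.20 × 25 = 5 points. At n = 390, SE = √(0.25/312 + 0.25/390) = 3.80 points, bias/SE = 1.32 and error = 26%. At n = 525, SE = 3.27 points, bias/SE = 1.53 and error = 33%.

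| Missing | g | Bias (points) | Error, 390 per arm | Error, 525 per arm |
|---|---|---|---|---|
| 20% v 0% | 0 | 0 | 5% | 5% |
| 20% v 0% | 10 | 2.0 | 8.2% | 9.4% |
| 20% v 0% | 25 | 5.0 | 26% | 33% |
| 14% v 6% | 0 | 0 | 5% | 5% |
| 14% v 6% | 10 | 0.8 | 5.5% | 5.7% |
| 14% v 6% | 25 | 2.0 | 8.3% | 9.4% |

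**Unequal missingness is not the cause.** The g = 0 rows show imbalance without bias. Balance does not protect either. Take 10% missing in each arm, MCAR in one arm, and a 25% response rate among the missing in the other, where the true rate is 50%. The observed rate in that arm is (0.50 − 0.10 × 0.25)/0.90 = 52.8%, a bias of 2.8 points. The error rate at 525 per arm is 14%.

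**Pooling over visits.** A simulation used 525 per arm, three visits, no true effect, dropout in one arm only and 400 replicates. It estimated the last-visit contrast from arm-by-visit means (independence working correlation; the plan names no working correlation). Missingness in the affected arm was about 0%, 17% and 31% across visits, a mean of 16%, so the total was (16 + 0)/2 = 8% and imputation would stay off.
- Dropout probability 34% after a non-response and 0 otherwise: bias 5.8 points, error 41%.
- Dropout probability 17% whatever the response: bias 0.0 points, error 5%.

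Monte Carlo standard errors are √(0.41 × 0.59/400) = 2.5 points and √(0.05 × 0.95/400) = 1.1 points. In the first case dropout depends on an observed earlier value, which an imputation model can use.

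**The case against.** The strongest reply is that the threshold is pre-specified, concerns only secondary analyses, and rarely matters unless missingness is both lopsided and strongly related to outcome. Much of this stands.

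- A reader might infer that unequal missingness between arms biases the comparison. It does not, because arm and time are in the model; the missingness must also be related to outcome within an arm.
- The 20% v 0% case is a knife edge. With equal arms, any missing observation in the second arm takes the total above 10% and imputation runs. The 25-point gap is also an assumption. At 14% v 6% with a 10-point gap, the error rate barely moves from 5%.
- A reader might infer that nothing is planned below the threshold. The tipping-point analysis has no such condition, so there is partial protection. It tests robustness to data missing not at random and does not correct the estimate, and Section 8.4.5 does not say which secondary outcomes it covers.
- A reader might infer that follow-up in general differs by setting. The documents do not support this: DLQI and topical-treatment surveys follow the same four-weekly schedule in both arms (Sections 6.2, 6.3), and Visit 2 is defined identically. What differs is the capture of session number, dose and treatment reactions, by home device or by site staff. Section 5.6 accepts that some devices will not be returned, while Section 5.7 relies on returned devices for verification. That is a one-arm route to missing treatment data, but nothing shows such loss to be outcome-related, and the binary-response calculation does not size it.

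What survives is that the gate measures quantity, while the plan's own stated condition concerns mechanism.

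**Conclusion.** The point holds as a modest improvement. Section 8.4.5 withholds its stated bias remedy on a criterion that cannot tell whether the bias is present. If dropout within an arm follows earlier non-response, a contrast below the gate can be materially wrong, chiefly at late visits.

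The possible size runs from nothing (no response gap) to an error rate of about a third (20% v 0%, 25-point gap, 525 per arm). It reaches about 41% in the simulated late-visit case. All of these rest on assumed response gaps or dropout mechanisms, and the documents give no basis for choosing among them.

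The scope is the repeated-measure GEE secondary and exploratory outcomes. A reader might infer that the trial's main conclusion, or every secondary outcome, is at risk. Neither follows: both co-primary outcomes count missing as failure, BSAxPGA is compared by linear regression at a single follow-up, and duration of response uses a weighted Cox model.

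**What to change.** Delete the 10% condition. Run the planned chained-equations imputation for every longitudinal GEE secondary outcome with missing data, and state that the imputation model contains arm, visit, skin type and earlier outcome values. Report the unimputed GEE beside it, with missingness tabulated by arm and visit. Keep the tipping-point analysis for data missing not at random and name the secondary outcomes it covers.

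A 10% trigger applied to each arm is not an adequate substitute. It would not fire at 10% v 0%, where a 25-point gap gives a bias of 0.10 × 25 = 2.5 points and, by the same formulas, an error rate of about 10% (390 per arm) to 12% (525 per arm).

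The cost is a little more analysis work, since the imputation is already specified; trial conduct does not change. The limit is that imputation corrects missingness explained by observed data (MAR). It does not correct data missing not at random.
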